6.4 Other Variables

6.4.1 SLICC/ACR Damage Index

The SLICC/ACR damage index is a validated instrument to assess damage, defined as irreversible impairment, continuously persistent for 6 months (ascertained by clinical assessment), occurring since the onset of lupus, and it is based on a weighted scoring system. This index records damage occurring in patients with SLE regardless of cause, with demonstrated content, face, criterion, and discriminant validity.⁴⁹ It will be performed on Days 0 and 180.

6.4.2 PROs

Patients should be encouraged to complete the PROs at the clinic at the beginning of the study visit prior to any clinical assessments. A member of the staff should be available if a patient requires further instruction and to review the PRO questionnaires for completeness prior to leaving the clinic. The PROs include the CCI and the CCI and will be assessed as specified in the Schedule of Assessments (Section 3.4).

CCI

CCI

6.5 Pharmacokinetic Assessments

During the MAD Phase 1b (all sites) and POC Phase 2 (select sites only) studies, blood samples for PK analysis of BOS161721 or placebo concentration will be collected according to Table 1 and Table 2.

Plasma concentrations of BOS161721 will be measured using a validated immunoassay. The PK parameters will be calculated from the plasma concentration actual time profiles.

6.6 Pharmacodynamic Assessments

Blood samples for PD parameters (plasma) will be collected at times indicated in the Schedule of Assessments (Section 3.4) for each of the following parameters:

- pSTAT3 (predose [trough] samples only Phase 1b)
- Antibodies: CCI
- Plasma complement (CCI)
- Plasma CCI and CCI
- Whole blood for leukocyte immunophenotype

6.7 Pharmacokinetic/Pharmacodynamic Relationship

Evidence of any PK/PD relationships will be evaluated between BOS161721 plasma concentrations and the available PD endpoints and biomarkers.

6.8 Protocol Deviations

Protocol deviations will be documented during the study.

7 STUDY DRUG MANAGEMENT

7.1 Description

7.1.1 Formulation

CCI [REDACTED]

CCI [REDACTED]

Additional information regarding dose preparation will be provided in a separate Pharmacy Manual.

7.1.2 Storage

All supplies of BOS161721 or placebo must be stored in accordance with the manufacturer's instructions. BOS161721 or placebo will be stored in a securely locked area, accessible to authorized persons only, until needed for dosing.

Information regarding storage and dose preparation will be provided in a separate Pharmacy Manual.

7.2 Packaging and Shipment

Investigational medicinal products will be supplied by Boston Pharmaceuticals, Inc. Investigational medicinal products will be packaged and labeled according to applicable local and regulatory requirements.

7.3 Dose and Administration

Details of dosing are provided in [Section 3.1](#).

Each unit dose will be prepared by a qualified staff member. The vials of investigational product (IP) will appear identical and will have a "blinded" label on the vials that will state CCI mg or placebo. When the site goes into the IWRS to request the patient kit(s), the IWRS will assign the

appropriate number of kits (regardless of assignment to placebo or active treatment) per the dose (ie, CCI [REDACTED]). If a patient is randomized to the placebo arm, they will receive the matching number of kits.

The designated staff member (or designee under the direction of the designated staff member) will dispense BOS161721 or placebo for each patient according to the protocol, randomization list, and Pharmacy Manual, if applicable.

After receiving sponsor approval in writing, the investigational site is responsible for returning all unused or partially used BOS161721 or placebo to the sponsor or designated third party or for preparing BOS161721 or placebo for destruction via incineration.

Further details are found in a separate Pharmacy Manual.

7.4 Accountability

The Principal Investigator or designee is responsible for maintaining accurate accountability records of BOS161721 or placebo throughout the clinical study. The drug accountability log includes information such as, randomization number, amount dispensed and amount returned to the pharmacy (if any). Products returned to the pharmacy will be stored under the same conditions as products not yet dispensed. The returned products should be marked as ‘returned’ and kept separate from the products not yet dispensed.

All dispensing and accountability records will be available for sponsor review after database lock procedures are completed. During safety monitoring, the drug accountability log will be reconciled with the products stored in the pharmacy.

7.5 Prohibited Concomitant Therapy

Prohibited concomitant medications are discussed in [Section 4.6](#) and [APPENDIX 4](#) and will be listed as protocol violations if taken when not permitted.

7.6 Compliance

Dosing will be performed by trained, qualified personnel designated by the principal investigator. The date and time of dosing will be documented on each dosing day. Comments will be recorded if there are any deviations from the planned dosing procedures.

8 STATISTICS

The following analyses are planned:

- An IA will be performed during the last cohort of the MAD phase to determine dose selection for the POC phase.
- The final analysis will be performed when all patients have completed the safety follow-up or withdrawn from the study.
- Safety analyses will be performed for DMC reviews throughout the study to evaluate dose escalation decisions and accumulating safety data. The frequency and details of the

content and format of the safety review meetings will be described in the SAP and/or DMC charter.

All statistical analyses will be performed using Statistical Analysis Software (SAS[®]) Version 9 or higher.

The following standards will be applied for the analysis unless otherwise specified. Data will be summarized descriptively by treatment and overall for each study phase. For the MAD phase, BOS161721 will be summarized overall and by each dose level, and placebo patients from each cohort will be combined. Select parameters will be summarized using patients from both study phases. Statistical testing will be performed on data from the Phase 2 study only.

Continuous data will be summarized using number, mean, standard deviation (SD), 25th and 75th percentiles, minimum, median, and maximum. Categorical data will be summarized by treatment group using frequency tables (number and percentage). Time to event data will be summarized using counts, medians, 25th and 75th percentiles, and standard error. All data will be listed for all patients.

Statistical inference will be based on a 2-tailed test with an overall 0.10 level of significance, unless stated otherwise.

The effects of noncompliance, background therapy use, treatment discontinuations, premature withdrawal from study and covariates will be assessed to determine the impact on the general applicability of results from this study. Exploratory analyses of the data will be conducted as deemed appropriate. Any deviations from the planned analyses will be described and justified in the final integrated CSR.

Protocol deviations and prohibited medications that define medication failures will be fully assigned and documented before database lock and unblinding.

Further details of the analysis, including the handling of missing data, transformations and other data handling procedures will be provided in the SAP.

8.1 Sample Size

Sample size in the Phase 1b study is based on operational consideration.

The sample size in the Phase 2 study is based on the primary endpoint, SRI-4 Response at Day 210. Approximately 156 additional patients will be randomized in a 2:1 ratio to BOS161721 versus placebo to achieve 132 evaluable subjects in the FAS. This assumes 24 subjects will drop prior to having received treatment and an evaluable post-baseline efficacy measure. Enrollment and randomization will be monitored in a blinded fashion and increased if needed to ensure at least 132 subjects are randomized into the FAS.

A total of 132 subjects randomized provides more than 80% power to detect a treatment difference of 25% in SRI-4 response rates at Day 210, based on a targeted 2-sided significance level of 10% and using a 2-sided Pearson's chi-squared test. This assumes of a response rate of 65% for BOS161721 and 40% for placebo, where missing data at Day 210 is carried forward

from most recent non-missing result and subjects are treated as a non-responder if a prohibited medication defined as a medication failure occurs.

8.2 Statistical Methods

8.2.1 Analysis Populations

The primary efficacy analysis will be based on the FAS, defined as all patients who receive at least 1 dose of study treatment and at have least 1 evaluable post-baseline efficacy evaluation. FAS analyses will be conducted on the basis of the randomized treatment.

A per protocol (PP) analysis set may be defined to exclude major protocol violations from the efficacy analysis. The PP Population will include all patients from the FAS except those with major violations to the protocol deemed to impact the analysis of the primary endpoint. These violations will be identified based on blinded data prior to study unblinding. PP analyses will be conducted on the basis of the randomized treatment.

Safety analyses will be based on the safety analysis set (SS), defined as all patients who receive at least 1 dose of study treatment. Safety analyses will be conducted on the basis of actual treatment received.

Pharmacokinetic analysis will be conducted on the PK analysis set, defined as the FAS with sufficient concentration data for the calculation of PK parameters.

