8.2.6 Pharmacokinetic and Pharmacodynamic Data

8.2.6.1 Analysis of Pharmacokinetic Data

PK parameters will be calculated from concentration data collected during the MAD Phase 1b using non-compartmental analysis and include the following:

- C_{\max} , T_{\max} , AUC, $t_{1/2}$, CL, V_d

The PK parameter data will be listed and summarized descriptively in tabular format.

If data permit, the following analyses will be performed for plasma BOS161721 concentration data:

- A listing of all plasma BOS161721 concentrations by patient at actual times post dose;
- A descriptive summary of plasma BOS161721 concentrations. Summary statistics of geometric mean, % coefficient of variation, standard deviation, median, minimum, and maximum will be tabulated by study days with PK assessments.

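### The PK analysis set is nested in the FAS, so a dosed Phase 1b patient with usable concentrations but no efficacy evaluation drops out of the PK summaries

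*Protocol*

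**What the plan says.** Section 8.2.1 (Analysis Populations) defines four sets.

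- **FAS:** "all patients who receive at least 1 dose of study treatment and at have least 1 evaluable post-baseline efficacy evaluation". Its treatment basis is explicit: "FAS analyses will be conducted on the basis of the randomized treatment".
- **Per-protocol set:** a subset of the FAS, with its own rule: "PP analyses will be conducted on the basis of the randomized treatment".
- **Safety set:** every patient with at least one dose. Its basis is also explicit: "Safety analyses will be conducted on the basis of actual treatment received".
- **PK set:** "Pharmacokinetic analysis will be conducted on the PK analysis set", which is "defined as the FAS with sufficient concentration data for the calculation of PK parameters". Nothing further is said about it, and no treatment basis is given.

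Section 8.2.6.1 states that "PK parameters will be calculated from concentration data collected during the MAD Phase 1b using non-compartmental analysis". It lists Cmax, Tmax, AUC, half-life, clearance and volume of distribution, and plans a by-patient listing of all concentrations and a descriptive summary by study day. Section 8 places the dose-selection interim analysis in the last Phase 1b cohort. The Version 3.0 text shown in the summary of changes for Section 3.1.2.2 names PK among the inputs to that decision.

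**The concern.** Whether a concentration profile is usable depends on dosing, sampling times and the assay. It does not depend on whether a disease-activity index was scored later. Building the PK set on the FAS adds an efficacy condition that has no pharmacokinetic purpose, while the set that would serve, all dosed patients, is defined in the same section. This is a rule the protocol itself fixes, not a detail deferred to the SAP.

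The PK parameters rest on Phase 1b alone, and its active cohorts are small, so losing one valid profile shows in a dose-level summary that feeds the choice of the Phase 2 dose. The missing treatment basis is a lesser gap beside it: the other three sets each have a rule and PK has none.

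**Working it through.** The plan states no figure for the PK set, so there is none to reproduce. The check is a reading of the definitions, followed by the size of the possible loss.

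**1. Membership.** Write D for dosed, E for at least one evaluable post-baseline efficacy evaluation, and C for sufficient concentration data.
- FAS = D and E.
- PK set as written = FAS and C = D and E and C.
- PK set on a safety-set base = D and C.
- Difference = D and C without E: dosed, enough concentrations, no efficacy evaluation.

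**2. Can that group exist?** The current schedule of assessments is in a part of the protocol not shown. In the Amendment 1 version reproduced later in the document (Section 4.3, Table 1), Phase 1b PK samples are taken 4, 8 and 24 hours after the Day 0 dose and on Days 7 and 15. The BILAG, SLEDAI-2K, PGA, joint count and CLASI first recur on Day 30. Section 1.2.3 of that version reports a median Tmax of 6 days. A patient lost after Day 15 would thus have samples around the first-dose peak and no efficacy evaluation. The Version 3.0 summary of changes to this table keeps the Day 7 and Day 15 columns and lists no change to those efficacy rows.

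**3. Cohort sizes.** The randomisation table in the summary of changes (Section 3.2) gives 6 patients at 5:1, 12 at 3:1 and 12 at 3:1.
- Active patients: 6 × 5/6 = 5, 12 × 3/4 = 9, 12 × 3/4 = 9; total 23.
- One excluded patient: 1/5 = 20% of the 20 mg cohort, or 1/9 = 11% of the 60 mg or 120 mg cohort.

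**4. How often?** The document gives no proportion of dosed patients without an efficacy evaluation. Taking q as an assumed proportion, the expected loss is n × q and the chance of at least one exclusion is 1 − (1 − q)^n:

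| Assumed q | Expected loss, n = 5 | Expected loss, n = 9 | Expected loss, n = 23 | Chance of at least one among 23 |
|---|---|---|---|---|
| 2% | 0.10 | 0.18 | 0.46 | 37% |
| 5% | 0.25 | 0.45 | 1.15 | 69% |
| 10% | 0.50 | 0.90 | 2.30 | 91% |

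These are upper figures for each q, because some of these patients would also fail the concentration condition.

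**5. Treatment basis.** Side by side: FAS randomised, per-protocol randomised, safety actual, PK not stated. The per-protocol set is also a subset of the FAS and still has its own sentence, so inheritance from the FAS cannot be assumed for PK.

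**6. Primary analysis.** The primary comparison uses the FAS, whose definition does not change, so its sample size and power are unaffected.

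**The case against.** Several points reduce the effect.

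- **End-of-treatment visit.** Section 6.5 of the Amendment 1 version asks for Day 180 procedures, and a last follow-up with Day 270 procedures, when a patient withdraws after dosing. Both columns include the disease-activity indices. An early leaver who attends enters the FAS; only one who attends neither visit stays excluded.
- **Replacement.** The Version 3.0 text for Section 3.1.1.1 allows Phase 1b patients who discontinue before adequate safety follow-up to be replaced. That protects cohort size but does not return the leaver's own data.
- **Limited information.** With a half-life of about 44 days, samples ending at Day 15 cannot reliably give half-life, or the clearance and extrapolated AUC that depend on it. Such a patient would contribute mainly Cmax and Tmax.
- **Listings.** All concentrations are listed by patient, and nothing shown confines the dose-selection review to the PK set. A listing is still not inclusion in the summary.

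Two stronger readings are tempting and fail. A reader might infer that PK will be analysed by randomised treatment, so that a kit error would place a profile under a dose not received. The text does not say so; the basis is simply unstated. A reader might also apply the 24 of 156 patients whom Section 8.1 expects to miss the FAS. That count is for Phase 2 and does not separate never-dosed patients, who have no concentrations to lose, while the PK parameters come from Phase 1b only.

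**Conclusion.** The definition is at fault, and the fault is minor. As written, a dosed Phase 1b patient with sufficient concentration data is excluded from the PK summaries if no post-baseline efficacy evaluation exists, for a reason unrelated to PK. One such patient costs 20% of the active patients in Cohort 1 or 11% in Cohort 2 or 3. How many there would be is unknown. Over an assumed 2% to 10% of dosed patients, the expected loss is about 0.5 to 2.3 of 23, and the end-of-treatment visit and the concentration condition pull this down.

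The conclusion on membership rests on Section 8.2.1 alone. That the exclusion can arise in practice rests on earlier-version schedules, since the current one is not shown. The treatment basis for PK should be recorded as not stated. No figure in the plan is shown to be wrong.

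**What to change.** In Section 8.2.1, replace the PK sentence with a definition of this kind: all Safety Set patients who received BOS161721 and have sufficient concentration data for at least one PK parameter, summarised by the treatment and dose actually received. Tying sufficiency to at least one parameter lets a short profile contribute Cmax and Tmax without being forced into half-life or clearance. The same sentence supplies the missing treatment basis.

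The cost is one sentence in the protocol and matching text in the SAP. It needs no extra patients, visits or samples.

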8.2.2 Demographics and Baseline Characteristics

Baseline and patient characteristics will be summarized using all randomized patients.

8.2.3 Primary Efficacy Endpoint(s)

The proportion of patients who achieve a SRI-4 response at Day 210 will be assessed via Pearson's chi-squared analysis. The primary efficacy endpoint will be analyzed using the FAS and if needed repeated in the PP analysis set. Missing values will be addressed by employing a last observation carried forward (LOCF) analysis. Other imputation methods may be employed as a sensitivity analysis and will be described in the SAP. Additional analyses exploring impact of baseline factors such as baseline disease severity, race, and other characteristics may be performed.

Patients that received prohibited medications or unallowable CS usage as described in [Section 4.6](#) will be considered "medication failures" and will be treated as non-responders for the primary efficacy analysis. Patients that received an allowable CS burst but having missing data at Day 210 will considered a medication failure and will be treated as non-responders for the primary efficacy analysis. The determination of medication failures will be reviewed using blinded data and finalized prior to unblinding.

The superiority of BOS161721 relative to placebo will be evaluated. If the proportion of SRI-4 responders for the selected POC dose in BOS161721 arm is higher than that of the placebo arm, then BOS161721 will be considered superior to placebo if the 2-sided p-value is less than or

equal to 0.10. Secondary and exploratory endpoints for this POC study will be evaluated based on the same statistical hypothesis.

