8.2.4 Secondary Efficacy Endpoint(s)

Binary efficacy endpoints will be assessed via Pearson's chi-squared analysis. Continuous efficacy endpoints will be assessed via analysis of variance (ANOVA) or analysis of covariance (ANCOVA) and treatment will be compared using the F-test. Repeated measures mixed models may be performed to evaluate data collected at each visit and overall. Time-to-event endpoints will be assessed via Kaplan-Meier methodology and treatment will be compared using the log-rank test. The secondary efficacy endpoints will be analyzed on the FAS and if needed repeated in the PP analysis set. Details including handling of missing data and "medication failures" will be available in the SAP.

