	
efficacy analysis. Patients that received an allowable CS burst but having missing data at Day 210 will considered a medication failure and will be treated as non-responders for the primary efficacy analysis. The determination of medication failures will be reviewed using blinded data and finalized prior to unblinding.
 
The superiority of BOS161721 relative to placebo will be evaluated. If the proportion of SRI-4 responders for the selected POC dose in BOS161721 arm is higher than that of the placebo arm, then BOS161721 will be considered superior to placebo if the 2-sided p-value is less than or equal to 0.10. Secondary and exploratory endpoints for this POC study will be evaluated based on the same statistical hypothesis.
	
randomization. Population is expected to be relatively homogenous, so Pearson chi-square as primary and secondary analyses may be conducted with factors for adjustment.

8.2.4	Secondary Efficacy Endpoint(s)	
	
Binary efficacy endpoints will be assessed via Pearson’s chi-squared analysis. Continuous efficacy endpoints will be assessed via analysis of variance (ANOVA) or analysis of covariance (ANCOVA) and treatment will be compared using the F-test. Repeated measures mixed models may be performed to evaluate data collected at each visit and overall. Time-to-event endpoints will be assessed via Kaplan-Meier methodology and treatment will be compared using the log-rank test. The secondary efficacy endpoints will be analyzed on the FAS and if needed repeated in the PP analysis set. Details including handling of missing data and “medication failures” will be available in the SAP.
	
Text updated to simplify and maintain consistency with binary endpoints. Allows more flexibility in handling missing data.

8.2.5	Analysis of Safety	
8.2.5.1	Safety Analysis	
	
Safety analyses will be performed on the SS. AE data will be coded to system organ class and preferred term using MedDRA. The number and percentage of patients experiencing any treatment-emergent AE, overall, and by system organ class an preferred term, will be tabulated. Treatment-emergent AEs will also be summarized by severity and relationship.
 
Concomitant medications will be coded using the WHO Drug dictionary. Observed values and changes from baseline in vital signs, ECG readings, and hematology and clinical chemistry parameters will be summarized at each individual visit.
	
8.2.6	Pharmacokinetic and Pharmacodynamic Data	

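### The primary test leaves out baseline SLEDAI-2K, which is already collected and built into SRI-4; the chi-squared is valid and adequately powered, but adjustment would be a free gain

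*Protocol*

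**What the plan says.** Section 8.2.3 of the protocol sets the primary analysis: "The proportion of patients who achieve a SRI-4 response at Day 210 will be assessed via Pearson's chi-squared analysis". The same section allows further analyses of baseline factors, disease severity among them, but does not require them. Section 8.2.4 applies the same chi-squared test to the other binary endpoints, and for the rest says "Continuous efficacy endpoints will be assessed via analysis of variance (ANOVA) or analysis of covariance (ANCOVA"), without saying which of the two applies when.

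Section 8.1 sizes the trial for this same test: "Approximately 156 additional patients will be randomized in a 2:1 ratio to BOS161721 versus placebo to achieve 132 evaluable subjects in the FAS". It continues: "A total of 132 subjects randomized provides more than 80% power to detect a treatment difference of 25"% in response rates, at a "targeted 2-sided significance level of 10"%, and "This assumes of a response rate of 65% for BOS161721 and 40% for placebo".

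The reason for an unadjusted test stands in Appendix 7, beside the wording adopted for Section 8.2.3. No stratification factors were used at randomisation, and "Population is expected to be relatively homogenous, so Pearson chi-square as primary"; secondary analyses with adjustment factors are permitted. Section 6.3.4.1 defines SRI-4 as a fall of at least 4 SLEDAI-2K points together with BILAG and PGA conditions.

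**The concern.** A patient's baseline SLEDAI-2K enters the arithmetic of the primary endpoint, because response is counted from it. Such a score may well predict response. If it does, a test that leaves it out has two weaknesses.

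The first is lower power than an adjusted test on the same data. The second is that, with about 44 placebo patients and no stratification, a chance difference in baseline disease activity feeds straight into the observed difference in response, and the primary analysis does nothing to remove it. This is one proof-of-concept decision at two-sided 0.10, so a poorly balanced draw could mislead in either direction.

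Lack of stratification explains why a stratified Cochran-Mantel-Haenszel test was dropped. It is no argument against regression adjustment, which needs no strata at randomisation.

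**Working it through.** **Inputs from Section 8.1.** FAS of 132 at 2:1, so 88 active and 44 placebo; response rates 0.65 and 0.40; two-sided alpha 0.10 (z = 1.645).

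**Step 1: reproduce the stated power.**
- Pooled rate = (44 × 0.40 + 88 × 0.65)/132 = 74.8/132 = 0.5667.
- Standard error under the null = √[0.5667 × 0.4333 × (1/44 + 1/88)] = 0.0915.
- Standard error under the alternative = √[0.24/44 + 0.2275/88] = 0.0897.
- Power = Φ[(0.25 − 1.645 × 0.0915)/0.0897] = Φ(1.11) = 86.6%.

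Exact enumeration gives 86.3%, or 82.9% with a continuity correction. All exceed 80%, so the protocol's claim holds.

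**Step 2: what adjustment could add.** The protocol gives no association between baseline SLEDAI-2K and SRI-4, so R² is an assumption. Approximating the effective sample size by 132/(1 − R²) and repeating Step 1:

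| Assumed R² | Effective N | Power | Gain (points) |
|---|---|---|---|
| 0 | 132 | 86.6% | 0 |
| 0.02 | 135 | 87.2% | 0.6 |
| 0.05 | 139 | 88.1% | 1.5 |
| 0.10 | 147 | 89.6% | 3.0 |
| 0.15 | 155 | 91.1% | 4.4 |
| 0.20 | 165 | 92.5% | 5.8 |

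**Step 3: check by simulation** (200,000 trials per setting). Chi-squared was compared with a Cochran-Mantel-Haenszel test on one 50/50 baseline factor. With response gaps of 20, 30 and 40 points between the two strata (R² about 0.04, 0.09, 0.16), power rises from about 86% to 87.6%, 89.3% and 91.5%. With no gap there is no gain. The false-positive rate in the favourable direction (nominal 5%) is 4.8 to 5.0% for both tests.

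A logistic model with one standardised continuous covariate, at assumed log-odds of 0.5 and 0.8 per SD, gives about 88% and 89 to 90%. Its false-positive rate depends on the test used: 5.0 to 5.3% for a score test and 5.2 to 5.6% for a likelihood-ratio test.

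**Step 4: chance imbalance.** The standard error of a standardised baseline difference is √(1/88 + 1/44) = 0.185. A difference above 0.2 SD in either direction therefore has probability of about 28%, and above 0.3 SD about 10%. Among simulated null trials with more than 0.3 SD in favour of active, the chi-squared false-positive rate is about 12% at log-odds 0.5 and 15% at 0.8. The adjusted test stays near 5%. With the imbalance against active and a true 25-point effect, chi-squared power falls to about 76% and 67%, while the adjusted test stays close to its overall level.

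**Step 5: continuous endpoints.** Let ρ be the baseline to follow-up correlation, with equal variances assumed. The variance of ANCOVA relative to ANOVA on the follow-up value is 1 − ρ²: 0.91, 0.75 and 0.51 at ρ = 0.3, 0.5 and 0.7. Relative to ANOVA on change it is (1 − ρ²)/[2(1 − ρ)] = (1 + ρ)/2: 0.65, 0.75 and 0.85. ANCOVA is the more precise in each case.

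**The case against.** The strongest reply is that nothing here is wrong. The trial was sized for exactly this test, the test holds its error rate, and its power exceeds the target. Chance imbalance is already inside that error rate when averaged over randomisations. The protocol gives a reason for its choice. All of this stands, and it rules out three stronger readings that a reader might infer.

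- *Power is lost, or the trial is underpowered.* It is not; power is lower only relative to an adjusted analysis.
- *Baseline activity is ignored.* Section 8 says covariate effects will be assessed, Section 8.2.3 names baseline severity for additional analyses, Section 8.2.4 names ANCOVA, and the summary text in Appendix 7 has ANCOVA adjusting for baseline where applicable.
- *The amendment removed a covariate adjustment from the primary test.* The superseded Cochran-Mantel-Haenszel analysis named neither strata nor covariates.

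Two further limits stand. SRI-4 also depends on BILAG, PGA and medication failure, so the 4-point rule alone does not tell us how prognostic baseline SLEDAI-2K is. And the expectation of a homogeneous population cannot be tested against the current entry criteria: the SLEDAI-2K and steroid limits visible in the document belong to superseded versions, and the current Section 4.4 is not in the part at hand.

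It may also be said that the statistical analysis plan, which is not shown, can settle all this. For ANOVA versus ANCOVA it can. For the primary test it cannot without departing from Section 8.2.3, which names the test outright.

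**Conclusion.** The point holds as a recommended improvement, not as an error. The planned chi-squared is valid, with about 86% power. Adjusting for baseline SLEDAI-2K would add nothing if the score is not prognostic, about 1.5 to 3 points of power at R² 0.05 to 0.10, and about 6 points at R² 0.20. That last figure equals 165 − 132 = 33 more evaluable patients. These gains rest on assumed prognostic strength, because the protocol offers none.

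Adjustment also removes most of the conditional bias when disease activity happens to differ between arms. Type I error is essentially unchanged, but some adjusted tests run slightly above nominal, so the deciding test has to be named. The case covers baseline SLEDAI-2K only; no other covariate, such as steroid dose, was evaluated. The ANOVA wording is the lesser part.

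**What to change.** Before unblinding, amend Section 8.2.3 so that the primary analysis compares SRI-4 response at Day 210 adjusted for continuous baseline SLEDAI-2K, with one named deciding test. An example is the standardised risk difference from a logistic model with treatment and baseline SLEDAI-2K, reported with its interval and with its p-value judged at two-sided 0.10. Keep the Pearson chi-squared as a supportive analysis. Section 8.1 can stay as it is, since its calculation is then conservative if the score is prognostic.

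In Section 8.2.4, replace the open choice between ANOVA and ANCOVA with ANCOVA on the baseline value for every continuous endpoint that has one.

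The cost is a change of wording and slightly more analysis work. It needs no further patients, visits or data.
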